## 5.12.1 Direct Measurement of Superficial Lesions

Imaging-based evaluation should always be done rather than clinical examination unless the lesion(s) being followed cannot be imaged but are assessable by clinical exam. Clinical assessment of lesions will only be considered measurable when they are superficial and ≥10mm dimension as assessed using callipers (e.g. skin nodules). For the case of skin lesions, documentation by colour photography, including a ruler to estimate the size of the lesion, should be used. As noted above, when lesions can be evaluated by both clinical exam and imaging, imaging evaluation should be undertaken since it is more objective and may also be reviewed at the end of the study.

While evaluation of lesions by PE is also of limited reproducibility, it is permitted when lesions are superficial, at least 10 mm size, and can be assessed using callipers. In general, it is preferred if subjects on clinical studies have at least one lesion that is measurable by CT. Other skin or palpable lesions may be measured on PE and be considered target lesions.

For response criteria assessment, documentation of palpable lesion size should be performed by photographing the lesion after circumscribing the lesion with a marker, delineating the long axis of the lesion with fingers, and placing a ruler adjacent to the lesion. This approach should be repeated at subsequent evaluation time points, with reference made to prior photographs to ensure that the same long axis measurements are performed consistently. The long axis diameter in millimetres should be used in the SOD calculation in combination with other target lesion(s).

#### 5.12.2 Planned Biopsy Analysis

Biopsies will be performed at baseline and Cycle 3 from injected lesion as well as from uninjected lesion.

Additional biopsy from superficial injected lesion will be performed on Cycle 1 Day 3 (48-72 hours) post AGI-134 administration. This biopsy is mandatory for superficial injected lesions

VS		PRIVILEGED & CONFIDENTIAL
Investigational Product: AGI-134		Protocol No. AGI-134.FIM.101
Phase: I/IIa	doses of AGI-134 in unresectable/metastatic solid tumours.	Version 6.1 31 May 2021

and is also requested for deep lesions, unless not considered in the best interest for the patient by the PI.

Procedures, collection, storage and shipping instruction will be provided in the *Administration* of AGI-134 and Tumour Biopsy Procedures in Study AGI-134.FIM.101 document.

The reason for a missing biopsy assessment should be documented within the eCRF. All efforts should be done in order to conduct all the biopsy assessments as required in the protocol.

Two core biopsies are required to be taken at each timepoint and from each lesion. All biopsies will be processed as Formalin-Fixed Paraffine-Embedded (FFPE) blocks.

#### 6 INVESTIGATIONAL PRODUCT

## 6.1 Identity of AGI-134

AGI-134 drug product is provided as 25 mg/mL in PBS, Solution for Injection. AGI-134 is filled and packed in clear Type I glass vials (DIN 2R), 1 mL per vial, with 13 mm serum stoppers and sealed with 13 mm caps.

## 6.2 Investigational Product Administration and Dosage

Each dose of AGI-134 will be administered intratumourally (IT) according to the longest tumour dimension and as described in the *Administration of AGI-134 and Tumour Biopsy Procedures in Study AGI-134.FIM.101* document.

#### 6.3 Manufacturing of Study Medication

AGI-134 is provided as a solution for injection administered via intratumoural injection. The drug product is a clear liquid essentially free of visible particles. The product is manufactured according to Good Manufacturing Practice (GMP) by

## 6.4 Distribution and Shipment of Study Medication

The investigational products will be packed and shipped in appropriate boxes. If, upon arrival at the clinical investigation site, the investigational product supplies appear to be damaged, the Clinical Research Associate (CRA) should be contacted immediately.

Each shipment of investigational product supplies for the study will be accompanied by a shipment form describing the contents of the shipment, product certificate of analysis, acknowledgement of receipt and other appropriate documentation. The shipment form will assist in maintaining current and accurate inventory records. The study staff will confirm the receipt of clinical supply to the CRA.

All study supplies should arrive at the pharmacy/Investigational site in sufficient quantity and in time to enable dosing as scheduled. The Sponsor or its representative must notify the PI prior to dispatch of drug supplies, with the anticipated date of their arrival.

20		PRIVILEGED & CONFIDENTIAL
Investigational Product: AGI-134	A Phase I/IIa, multicentre, two-parts, open label study designed to evaluate the safety and tolerability of escalating	Protocol No. AGI-134.FIM.101
Phase: I/IIa		Version 6.1 31 May 2021

## 6.5 Storage, Dispensing and Return of the Investigational Product

Investigational product dispensing and accountability records (how much investigational product was dispensed to each subject) should be kept by the Pharmacy and by the PI or designee. The CRAs must periodically check the investigational product supplied to ensure expiry date and sufficient amount of investigational product and be sure that drug accountability is being performed at each visit and the drug accountability logs are maintained.

The investigational product must be kept in a secure area with a limited-access to the investigational product by designated study personnel.

Only trained personnel under the supervision of either the PI or the local pharmacist are authorised to dispense and administer investigational product to participating subjects.

Further details and instructions will be provided in the Pharmacy Manual.

AGI-134 solution for injection 25 mg/1 mL vials should be stored at refrigerated conditions (2-8°C), protected from light and at vertical, upright position.

## 6.6 Accountability and Compliance of Investigational Product

Each delivery must be acknowledged by the site's pharmacist (or authorised study team member responsible for the investigational product) by filling in the receipt record form and returning it by fax/email to the Sponsor or designee. Accurate, complete and timely documentation of investigational product distribution will be maintained by the pharmacy and the study staff of the investigational site which may include confirmation of receipts of clinical supply, drug accountability logs and other forms.

The site's pharmacist (or authorised study team member responsible for the investigational product) is responsible for ensuring the supervision of the storage and allocation of these supplies, which will be forwarded to the PI at the appropriate time before administration. The PI will dispense investigational product only to subjects enrolled in the study.

Drug accountability records must be maintained by the site at all times. At the last study visit, all used and unused investigational product will be collected, and drug accountability will be performed by the study staff.

During the study, drug orders, records of investigational product receipts, dispensing records and inventory forms located at the site will be checked and reconciled by the CRA periodically during and at the end of the study.

The subject number, the date, batch number/pack number and quantity of investigational product used by the subject will be checked for correctness and recorded on the appropriate accountability forms. Unused drug supplies will be returned to the Sponsor. At the end of the study, all clinical supplies and the corresponding accountability forms must be returned to the Sponsor, the CRA or designee for reconciliation or destruction. A photocopy of these records must be kept at the clinical investigation site.

20		PRIVILEGED & CONFIDENTIAL
Investigational Product: AGI-134	A Phase I/IIa, multicentre, two-parts, open label study designed to evaluate the safety and tolerability of escalating	Protocol No. AGI-134.FIM.101
Phase: I/IIa		Version 6.1 31 May 2021

## 6.7 Concomitant Therapy

At the Screening visit, relevant treatments currently taken by the subject will be recorded in the subject's eCRF including treatment's name, indication, dose, total daily dose and start- and stop dates.

Any medications (including prescription, over-the-counter [OTC], herbal supplements and other health store-type products) to be taken during the study must be approved by the PI.

Concomitant medication use will be recorded from Screening through the Termination visit. Treatment provided for the subject's disease, during Long-Term Follow-Up will be captured as part of the duration of response and survival status assessment. The following information should be recorded: Treatment's name (generic, if possible) dose and start- and stop dates.

All concomitant medications received from 30 days before the Screening visit through 30 days after Termination/ET visit should be recorded. Concomitant medications administered more than 30 days after Termination/ET visit should be recorded for SAEs and events of clinical interest (ECIs).

Medications specifically prohibited in the Exclusion Criteria are not allowed during the ongoing study. If there is a clinical indication for any medication specifically prohibited during the study, the study continuation should be discussed with the Sponsor's Medical Monitor. The PI should discuss any questions regarding this with the Sponsor's MM. The final decision on any supportive therapy rests with the PI and/or the subject's primary physician. However, the decision to continue the subject's study therapy requires the agreement of the PI, the Sponsor and the subject.

#### 6.7.1 Allowed Medications

All treatments that the PI considers necessary for a subject's welfare may be administered at the discretion of the PI in keeping with the community standards of medical care. All concomitant medication will be recorded on the eCRF including all prescription, OTC, herbal supplements, and IV medications and fluids. If changes occur during the study period, documentation of drug dosage, frequency, route and date may also be included in the eCRF.

#### 6.7.2 Prohibited Concomitant Medications

Subjects are prohibited from receiving the following medications during the Core study, beginning at Screening Visit until Termination Visit (week 54) or disease progression, whichever comes first:

- Systemic glucocorticoids for any purpose other than to modulate an event of suspected immunologic aetiology or for systemic and local reactions secondary to the treatment. The use of physiologic doses of corticosteroids may be approved after consultation with the Sponsor. Note: Inhaled steroids are allowed for management of asthma, and dermatological formulations are allowed to reduce the intensity of injection-site reactions.
- Therapy for the disease under study:
  - Antineoplastic systemic chemotherapy or biological therapy
  - Immunotherapy or other therapy not specified in this protocol

20		PRIVILEGED & CONFIDENTIAL
Investigational Product: AGI-134		Protocol No. AGI-134.FIM.101
Phase: I/IIa		Version 6.1 31 May 2021

- Chemotherapy not specified in this protocol
- Investigational agents other than AGI-134
- Radiation therapy: localised radiation therapy may be considered on an exceptional case by case basis after consultation with the Sponsor.

During the Long-Term Follow-Up period, subjects who have no disease progression should be followed up until disease progression, new cancer treatment or withdraw consent. Subjects may receive other treatments following progression and/or upon investigator's and/or the subject's primary physician decision.

For subjects who, in the assessment of the PI, require the use of any of the aforementioned treatments for clinical management, the study continuation should be discussed with the Sponsor's Medical Monitor.

The Exclusion Criteria describes other medications that are prohibited in this study.

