# Long-Term Follow-Up

All subjects will be contacted by phone every 9 weeks after Termination/Early Termination for 5 years to follow-up on duration of response and survival status.

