# Ongoing Safety Assessment and Dose-Limiting Toxicity

AEs will be reported from the time of informed consent signature Up to 30 days after the last dose of study drug or until the initiation of new anticancer treatment, whichever is sooner. SAEs will be reported until 90 days after the last dose of study drug, or until the initiation of new anticancer treatment, whichever is sooner.

agalin A subsidiary of Bit	OLINERX	PRIVILEGED & CONFIDENTIAL
Investigational Product: AGI-134		Protocol No. AGI-134.FIM.101
Phase: I/IIa	doses of AGI-134 in unresectable/metastatic solid tumours.	Version 6.1 31 May 2021

Study Assessments	The period considered for DLT assessment is defined for Part 1 and Part 2, as the time from the first dose administration of AGI-134 and up to the end of the first cycle of therapy (e.g., Cycle 1/Day 1 through to Cycle 1/Day 21).  After the DLT assessment period, data will be assessed an ongoing manner during the study. All AEs should be captured within the eCRF; AEs reported beyond the DLT period will not be considered for the DLT assessment.
	General instructions before study drug administration
	The following instructions should be followed before AGI-134 administration:
	
 
AGI-134 should only be administered when personnel and therapies are immediately available for the treatment of hypersensitivity reactions, should they occur. This should include having an open IV cannula and fluid therapy readily available.
 

	
 
Hypovolaemia, if present, should be corrected prior to administration of AGI 134 according to the study site standard of care.
 

	
 
For patients who receive routine anti-hypertensive medication, these medications should be withheld in the 24 hours prior to injection of AGI-134.
 

	Recommendations for patients who experience systemic reactions related to study drug are detailed in section 5.7.
Study	The duration of core study participation is 54 weeks.
Duration	A Termination visit will be performed for all subjects on Week 54. Long-term follow-up will continue for all subjects for up to 5 years.
	The study consists of the following study periods:
	Screening Period: up to 28 days
	Core Study: up to 54 weeks
	Long-Term Follow-Up: Following Termination/Early Termination visit, a follow-up telephone call will be performed to all subjects every 9 weeks up to 5 years in order to assess duration of response and survival.
Planned	Part 1: Up to 24 subjects.

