## 4.5 Removal, Replacement or Early Withdrawal of Subjects from Therapy or Assessment

Subjects are free to discontinue the investigational product and/or their participation in the study at any time and without prejudice to further treatment. The PI must withdraw any subject from the study if that subject requests to be withdrawn, or if it is determined that continuing in the study would result in a significant safety risk to the subject. Subjects that discontinue the investigational product will continue to participate in the Long-Term Follow-up of the study for 5 years, unless they withdraw their consent to continue their participation in the study as well.

Subjects withdrawn from the study prior to the Baseline visit, prior to first injection of AGI-134 or before completion of the DLT assessment period (see Section 3.1.1) will be replaced by the PI to achieve the appropriate number of subjects, regardless of the reason for withdrawal. All data, regardless of DLT period completion or not, will be part of the safety cohort assessment.

If a subject discontinues from the study during the DLT assessment period for any reason other than safety, a replacement subject may be enrolled if deemed appropriate by the PI and Sponsor in order to reach the target number for DLT assessment. Subjects who discontinued the study during the DLT period because of progression will not be considered for DLT assessment; however, they will be counted as having progressed for the efficacy analysis. The replacement subject will be assigned with a unique subject number.

The subject's use of investigational product may be discontinued for any of the following reasons:

- Investigational product toxicity (adverse drug reaction)
- Death
- · Request of regulatory agency
- · Sponsor's request
- PI's request: Investigator decides that withdrawal from the study is in the best interest of the subject
- · Withdrawal of consent by the subject
- Disease Progression
- Female subject who becomes pregnant
- Lost to follow-up

agalin A subsidiary of Bio	nnune DLINERX	PRIVILEGED & CONFIDENTIAL
Investigational Product: AGI-134		Protocol No. AGI-134.FIM.101
Phase: I/IIa		Version 6.1 31 May 2021

- · Subject is non-compliant with study procedures/study protocol
- Other

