## 5.5 Long-Term Follow-Up

All subjects, including early terminated subjects, will be contacted by phone every 9 weeks (±7 days) after Termination/ET visit (Week 54). This Follow-Up will continue for 5 years. During these phone calls, subjects will be asked to provide an update about disease status and post-study anti-cancer therapy received. During the first Long-Term follow-up visit, subjects should be questioned regarding the occurrence of AEs/SAEs and the outcome of any AEs/SAEs that were ongoing at the Termination/Early Termination visit. However, only AEs that occurred up to 30 days after the last dose of study drug and SAEs that occurred up to 90 days after the last dose of study drug will be recorded in the eCRF (see sections 7.1 and 7.2.2 for details). In case of death, every effort should be done in order to capture the date and reason for death. All the data will be collected and entered within the eCRF.

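### Section 6.7.2 and the matching Synopsis text end Long-Term Follow-Up at progression or new treatment for progression-free subjects, while the rest of the protocol calls every subject for 5 years; survival censoring may become informative

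*Combined protocol and SAP*

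**What the plan says.** Two places carry a stop rule. Section 6.7.2 (Prohibited Concomitant Medications) and the corresponding Synopsis text say that, during Long-Term Follow-Up, "subjects who have no disease progression should be followed up until disease progression, new cancer treatment or withdraw consent".

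The other places describe a fixed 5-year follow-up:

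- Synopsis, Long-Term Follow-Up: every subject is "contacted by phone every 9 weeks after Termination/Early Termination for 5 years to follow-up on duration of response and survival status".
- Synopsis, Study Duration: "Long-term follow-up will continue for all subjects for up to 5 years".
- Section 5.5: "All subjects, including early terminated subjects, will be contacted by phone every 9 weeks", and "This Follow-Up will continue for 5 years". At these calls "subjects will be asked to provide an update about disease status and post-study anti-cancer therapy received", and the date and reason for any death are to be captured.
- Section 4.5: subjects who discontinue the product, with progression among the listed reasons, "will continue to participate in the Long-Term Follow-up of the study for 5 years, unless they withdraw their consent".
- Section 6.7: treatment given for the disease during Long-Term Follow-Up is recorded as part of the response-duration and survival assessment.
- Appendix A: Table 6 labels the Long-Term Follow-Up column as a survival call and marks post-study therapy and survival status. Table 7 marks post-study therapy and a combined row for disease and survival status.

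**The concern.** Taken at its word, the 6.7.2 sentence treats subjects differently according to outcome. A subject who progressed at Week 9 is called for survival for 5 years. A subject who first progresses at Week 70 leaves follow-up at that point. A subject who starts a new cancer treatment before progressing also leaves.

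In unresectable or metastatic disease the risk of death would be expected to rise after progression, so this censoring is unlikely to be independent of survival. With approximately 15 sites, some may follow 6.7.2 and others Section 5.5, and survival would then be captured differently by site. The calls are the only scheduled contact in this period, so lost information may not be recoverable.

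**Working it through.** **1. Setting the passages side by side.** The plan states no survival rate, hazard or survival censoring rule, so it has no figure to reproduce. The first check is of the text.

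- *Who and how long.* The Synopsis and Section 5.5 say all subjects and 5 years (up to 5 years under Study Duration). Section 6.7.2 gives three earlier stops for subjects without progression.
- *What is collected.* Section 5.5 asks about post-study therapy, and Section 6.7 records it within the survival assessment. Both presuppose contact after new treatment, which 6.7.2 makes a stop.
- *Can part of the follow-up stop alone?* Long-Term Follow-Up has no separate imaging stream. One telephone call collects disease status, therapy and survival, so ending follow-up ends survival capture.
- *The consent stop.* Section 6.7.2 lists withdrawal of consent beside progression and new treatment. In Section 4.5 withdrawal of consent ends follow-up altogether, so a site can fairly read 6.7.2 as a full stop.

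**2. Possible size (illustration).** From the documents: entry to Long-Term Follow-Up at Week 54, follow-up for 5 years, and about 35 subjects in Part 2. Assumed, because the documents give nothing:

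- exponential times
- median PFS of 3, 6 or 12 months
- median survival after progression of 6, 12 or 18 months
- death hazard before progression h0 = 0.005 per month.

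Here PFS means time to progression, with hazard λ = ln 2 / median, and the hazard of death after progression is h1 = ln 2 / median. Week 54 is T = 54/52.18 × 12 = 12.42 months.

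*Share alive and progression-free at Week 54:* exp(−(λ + h0)T).

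- Median PFS 3 months: exp(−0.2360 × 12.42) = 5.3%, about 2 of 35.
- Median PFS 6 months: exp(−0.1205 × 12.42) = 22.4%, about 8 of 35.
- Median PFS 12 months: exp(−0.0628 × 12.42) = 45.9%, about 16 of 35.

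*Survival with full follow-up,* with a = λ + h0:

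S(t) = exp(−at) + [λ/(h1 − a)] × [exp(−at) − exp(−h1·t)].

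*Kaplan-Meier survival under the literal rule.* Up to Week 54 it equals S(t). After that the estimated hazard is [F(u)·h0 + E(u)·h1] / [F(u) + E(u)]. F(u) = exp(−au) is the progression-free group. E(u) = E(T)·exp(−h1(u − T)) is the group that progressed before Week 54 and stays under observation.

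Example with both medians 12 months: λ = h1 = 0.05776 and a = 0.06276. At 36 months exp(−at) = 0.1044 and exp(−h1·t) = 0.1250. So S = 0.1044 + (0.05776/−0.005) × (0.1044 − 0.1250) ≈ 0.342. A simulation of 400,000 subjects gives 34.3%. Under the literal rule the simulation gives 41.1% and the formula 41.0%.

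Simulated 36-month survival, full follow-up against literal rule (the formulas agree within 0.2 point):

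| Median PFS (months) | Median survival after progression (months) | Full | Literal 6.7.2 | Difference (points) |
|---|---|---|---|---|
| 3 | 6, 12, 18 | 3.0%, 16.2%, 29.3% | 3.0%, 16.2%, 29.4% | 0 to 0.1 |
| 6 | 6 | 7.3% | 10.1% | +2.8 |
| 6 | 12 | 21.8% | 22.8% | +1.0 |
| 6 | 18 | 34.8% | 35.5% | +0.7 |
| 12 | 6 | 20.1% | 34.5% | +14.4 |
| 12 | 12 | 34.3% | 41.1% | +6.8 |
| 12 | 18 | 45.1% | 49.3% | +4.2 |

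**3. Direction.** The table gives early and late progressors the same hazard after progression. Now lower the hazard of those who progress after Week 54, keeping the median for early progressors at 12 months:

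- Half the hazard, median PFS 12: 40.8% full, 41.0% literal, about no bias.
- Half the hazard, median PFS 6: 26.4% full, 22.9% literal, biased downward.
- A quarter of the hazard, median PFS 6: 29.8% full, 23.0% literal, biased downward.

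The model covers censoring at progression only. Censoring at new treatment can act in either direction. Subjects who terminate early without progression would also fall under the rule and are not modelled.

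**The case against.** The strongest reply is that the intended design is clear. The sentence sits under prohibited medications, and the next one says when other treatments may be given, so its purpose seems to be the timing of new therapy. Follow-up is set out consistently in the Synopsis, Sections 4.5 and 5.5 and both schedule tables, and a site would have to override all of these. This makes 5-year follow-up of all subjects the likely intent. It does not remove the conflict: no passage confines the sentence to disease status, and it appears twice.

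Three stronger readings are tempting, and the documents do not support them.

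- *Survival will be overestimated.* Upward is the expected direction, but step 3 shows that it can vanish or reverse.
- *The error is very large.* For subjects progression-free at Week 54 taken alone, stopping at progression gives exp(−0.005 × 36) = 83.5% at 36 months, far above any plausible true value. That figure only restates the assumed death hazard before progression, for a subset. In the whole cohort, early progressors stay under observation and the effect is that in the table.
- *A planned survival analysis is compromised.* The list of exploratory endpoints and any survival censoring rule are not visible. Survival status is collected, but a formal analysis cannot be confirmed, and the visible primary endpoint is safety, MTD and RP2D.

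**Conclusion.** The contradiction stands on the text alone and needs no assumption: Section 6.7.2 and the matching Synopsis text cannot be applied together with Section 5.5. If sites apply the stop literally, and those subjects are censored there, the censoring is informative and confined to subjects who entered Long-Term Follow-Up without progression.

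The likely bias is upward. With equal hazards after progression it is about 0 points in 36-month survival at median PFS 3 months, 0.7 to 2.8 at 6 months and 4.2 to 14.4 at 12 months. It is negligible if nearly all subjects progress before Week 54 and grows with the share who do not. These sizes rest wholly on assumed hazards. The primary safety and dose-finding conclusions are not affected. The reason to act is that survival data could be lost, unevenly by site, through a wording conflict that is easily removed.

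**What to change.** In Section 6.7.2 and the matching Synopsis text, state that progression or new cancer treatment does not end the Long-Term Follow-Up calls. All subjects continue to be called as in Section 5.5, for disease status, post-study anti-cancer therapy and survival, for 5 years or until death or withdrawal of consent.

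If the present sentence is kept, limit it to the period used to determine progression and duration of response. It should not be turned into a rule that stops collecting disease status at progression or new treatment, because Section 5.5 asks for disease status at the calls over the 5 years.

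The cost is one sentence in two places, submitted as a protocol amendment under Section 9.9. It adds no contact, since the 9-weekly schedule already implies about 5 × 52.18 / 9 = 29 calls per subject. It changes no treatment rule.
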